6.3.7 Day 7 to Day 14/End of Treatment Visit

Patients will be treated for 7 days (28 doses), with a prolongation of therapy up to 14 days if clinically indicated in patients with concurrent bacteremia. If EOT occurs on Day 7, Day 7 study procedures may be considered the EOT Visit study procedures. Day 7 to Day 14 study procedures are only required if the patient receives IV study treatment on Day 7 to Day 14. If EOT has already occurred, study procedures are not required to be performed. The EOT Visit will be completed on the final dosing day or the following day (allowing for a 1-day window to complete EOT procedures).

The following procedures will be performed at Day 7 to Day 14 and at the EOT Visit:

- Record concomitant medications;
- Perform a complete physical examination, including weight (Day 7 and EOT Visit only);
- Perform a limited physical examination (Day 8 to Day 14 only);
- Obtain vital signs, including blood pressure, heart rate, and respiratory rate;
- Assess clinical signs and symptoms;
- Assess clinical outcome (Day 7 and EOT Visit only);
- Perform pregnancy test for women of childbearing potential only (EOT Visit only);
- Collect blood sample for:
 - Serum chemistry (Day 7 and EOT Visit only);
 - Hematology (Day 7 and EOT Visit only); and
 - Blood cultures, if applicable;
- Collect urine sample by clean-catch midstream or other appropriate method that minimizes risk of bacterial contamination for:
 - Urinalysis (Day 7 and EOT Visit only); and
 - Urine cultures;

- Administer imipenem/cilastatin;
- Administer study drug; and
- Assess adverse events.

6.4 Test-of-Cure Visit

The TOC Visit will occur 7 days (± 1 day) after the EOT Visit.

The following procedures will be performed at the TOC Visit:

- Record concomitant medications;
- Perform a limited physical examination;
- Obtain vital signs, including blood pressure, heart rate, and respiratory rate;
- Assess clinical signs and symptoms;
- Assess clinical outcome;

Note: if a patient is a clinical failure at EOT, the patient is automatically considered a failure at the TOC and LFU Visits, and the assessment of clinical response by the Investigator should be listed as “failure at EOT.”

- Collect blood samples for:
 - Serum chemistry;
 - Hematology; and
 - Blood cultures, if applicable;
- Collect urine sample by clean-catch midstream or other appropriate method that minimizes risk of bacterial contamination for:
 - Urinalysis; and
 - Urine cultures; and
- Assess adverse events.

6.5 Late Follow-up Visit

The LFU Visit will occur 7 days (± 2 days) following the TOC Visit. The LFU Visit should be performed as an in-office visit; however, if the patient is unable to attend the LFU Visit at the site, the patient may be contacted by telephone call for follow-up assessment of concomitant medications, clinical signs and symptoms, and adverse events.

The following procedures will be performed at the LFU Visit:

- Record concomitant medications;
- Perform a limited physical examination;
- Obtain vital signs, including blood pressure, heart rate, and respiratory rate;
- Assess clinical signs and symptoms;

- Assess clinical outcome;
 - Note: if a patient is a clinical failure at EOT, the patient is automatically considered a failure at the TOC Visit and LFU Visit, and the assessment of clinical response by the Investigator should be listed as “failure at EOT or TOC.”
- Collect blood samples for:
 - Serum chemistry;
 - Hematology; and
 - Blood cultures, if applicable;
- Collect urine sample by clean-catch midstream or other appropriate method that minimizes risk of bacterial contamination for:
 - Urinalysis; and
 - Urine cultures; and
- Assess adverse events.

6.6 Withdrawal Procedures

For patients who are withdrawn from the study prior to completion of study drug, complete an EOT Visit at the time of study termination. For patients who are withdrawn from the study after the EOT Visit but prior to completion of the study, complete the next scheduled visit (either TOC or LFU Visit) at the time of study termination.

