Although local susceptibility testing is not a requirement, when local susceptibility testing indicates non-susceptibility to imipenem (eg, intermediate susceptibility or resistance to imipenem) but the patient is stable or clinically improving, the patient should remain on study drug at the discretion of the Investigator. Prior to discontinuation from study drug, the Investigator should discuss such cases with the Medical Monitor.

Day 1 is defined as the first day of study drug administration. The subsequent study days are defined by the number of calendar days thereafter. The duration of antibiotic treatment with study drug therapy will be 7 days (28 doses), with a prolongation of therapy up to 14 days if clinically indicated in patients with concurrent bacteremia.

All patients should receive at least 8 doses of IV study drug before the Investigator considers the patient to be a clinical failure and discontinues the patient from study drug therapy. No oral switch option is allowed. Patients who withdraw from study drug dosing should perform all End of

Treatment (EOT) Visit procedures and should be followed through the Late Follow-up (LFU) Visit for safety assessments, even if they withdraw from dosing due to clinical failure.

Throughout the study, all patients will be monitored for signs and symptoms of cUTI or AP and the occurrence of adverse events. Laboratory data, including chemistry panels, complete blood counts, and samples for urine and blood cultures, as well as electrocardiograms (ECGs), will be collected from all patients at specified times throughout the study.

Sparse PK sampling (ie, a total of 5 samples per patient) will be performed to refine the population PK model. To maintain the blind, PK samples will be collected from both treatment groups. Samples obtained from the ETX2514SUL group will be analyzed using a validated assay by a central bioanalytical laboratory.

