4.3 Withdrawal Criteria

Participation of a patient in this clinical study may be discontinued for any of the following reasons:

- The patient withdraws consent or requests discontinuation from the study for any reason;
- Occurrence of any medical condition or circumstance that exposes the patient to substantial risk and/or does not allow the patient to adhere to the requirements of the protocol;
- Any SAE, clinically significant adverse event, severe laboratory abnormality, intercurrent illness, or other medical condition which indicates to the Investigator that continued participation is not in the best interest of the patient;
- Pregnancy;
- Requirement of prohibited concomitant medication;
- Patient failure to comply with protocol requirements or study-related procedures; or
- Termination of the study by the Sponsor or the regulatory authority.

For patients in whom the creatinine clearance drops below 70 mL/min after baseline, the Investigator should repeat serum creatinine at the local laboratory once they receive the abnormal laboratory result to confirm the value. The Investigator may withdraw the patient from the study when a dose adjustment for imipenem is necessary or when patient safety is at risk. However, if the Investigator believes that the creatinine clearance decrease is not clinically significant or will quickly reverse, the Medical Monitor will be contacted to discuss if the patient may continue in the study or should be withdrawn.

If a patient withdraws prematurely from the study due to the above criteria or any other reason, study staff should make every effort to complete the full panel of assessments scheduled for the EOT Visit, and the patient should be followed through the LFU Visit. If a patient withdraws after the EOT Visit, study staff should make every effort to complete the full panel of assessments scheduled for the study visit following the date of withdrawal (TOC Visit or LFU Visit), as applicable. The reason for subject withdrawal must be documented in the electronic case report form (eCRF).

In the case of patients lost to follow-up, attempts to contact the subject must be made and documented in the patient's medical records.

Withdrawn subjects will not be replaced.

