Two sets of blood culture samples must be obtained from 2 separate venipuncture sites at Screening. Each set is collected from a separate venipuncture and consists of 1 aerobic and 1 anaerobic blood culture bottle. Each set of blood cultures should be collected by direct venipuncture from independent sites approximately 15 to 30 minutes apart. If baseline blood cultures are positive and not considered contaminated, repeat blood cultures should be obtained daily until negative or if the patient is a treatment failure. To avoid unnecessary blood draws, the

Investigator may wait until the result of the prior blood culture is known before performing the next blood culture.

The local laboratory will culture each sample for organism identification, quantification (urine only), and susceptibility testing. Any organism isolated from the blood or urine will be identified by genus and species by the local laboratory. Potential pathogen(s) cultured at the local laboratory from urine or blood samples will be sent to a designated central laboratory for confirmation of identification and susceptibility testing results.

Only those baseline potential pathogens that grow in the urine at $\geq 10^5$ CFU/mL and deemed not to be contaminants will be sent to the central laboratory. Potential pathogens that grow in both the urine and blood will also be sent to the central laboratory prior to randomization.

For post-baseline urine cultures, only those potential pathogens that grow at $\geq 10^3$ CFU/mL and deemed not to be contaminants will be sent to the central laboratory.

Although local susceptibility testing is not a requirement, when local susceptibility testing indicates non-susceptibility to imipenem (eg, intermediate susceptibility or resistance to imipenem) but the patient is stable or clinically improving, the patient should remain on study drug at the discretion of the Investigator. Prior to discontinuation from study drug, the Investigator should discuss such cases with the Medical Monitor.

When a patient's urine culture grows only Gram-positive organisms, but the patient is clinically improving, the patient may remain on study drug without additional Gram-positive antibiotic coverage at the Investigator's discretion. Patients who are not clinically improving should be discontinued from study drug at the discretion of the Investigator but should remain in the study to complete all study assessments.

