8 SAFETY ASSESSMENTS

8.1 Adverse Events

An adverse event is defined as any untoward medical occurrence in a clinical investigation patient administered a pharmaceutical product, which does not necessarily have a causal relationship with this treatment. An adverse event can therefore be any unfavorable and/or unintended sign (including an abnormal laboratory finding), symptom, or disease temporally associated with the use of an investigational medicinal product, whether or not related to the investigational medicinal product. All adverse events, including observed or volunteered problems, complaints, or symptoms, are to be recorded on the appropriate eCRF.

Adverse events, which include clinical laboratory test variables, will be monitored and documented from the time of informed consent until study participation is complete. Subjects should be instructed to report any adverse event that they experience to the Investigator. Beginning at Screening, Investigators should make an assessment for adverse events at each visit and record the event on the appropriate adverse event eCRF.

Wherever possible, a specific disease or syndrome rather than individual associated signs and symptoms should be identified by the Investigator and recorded on the eCRF. However, if an observed or reported sign or symptom is not considered a component of a specific disease or syndrome by the Investigator, it should be recorded as a separate adverse event on the eCRF. Additionally, the condition that led to a medical or surgical procedure (eg, surgery, endoscopy, tooth extraction, or transfusion) should be recorded as an adverse event, not the procedure.

Any medical condition already present at Screening should not be reported as an adverse event unless the medical condition or signs or symptoms present at baseline changes in severity or seriousness at any time during the study. In this case, it should be reported as an adverse event.

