9.2.2.1 Primary efficacy analysis

The primary efficacy endpoint for this study is the proportion of patients with an overall success (clinical cure and microbiologic eradication) in the m-MITT Population at the TOC Visit.

Patients will be programmatically categorized as a success, failure, or indeterminate response. Patients with missing data or who are lost to follow-up are defined as indeterminate for the primary analysis and are included in the denominator for the calculation of overall success rate. Thus, patients with an indeterminate outcome are considered failures for the primary analysis. The number and percentage of patients in each treatment group with an overall success, failure, and indeterminate response will be determined. A 2-sided 95% confidence interval (CI) for the observed difference in the overall success rates (EXT2514SUL group minus placebo group [background imipenem/cilastatin therapy]) will be calculated using a continuity-corrected Z-statistic.

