Day 1 is defined as the first day of study drug administration. The subsequent study days are defined by the number of calendar days thereafter. The duration of antibiotic treatment with study drug therapy will be 7 days (28 doses), with a prolongation of therapy up to 14 days if clinically indicated in patients with concurrent bacteremia.

All patients should receive at least 8 doses of IV study drug before the Investigator considers the patient to be a clinical failure and discontinues the patient from study drug therapy. No oral switch option is allowed. Patients who withdraw from study drug dosing should perform all End of Treatment (EOT) Visit procedures and should be followed through the Late Follow-up (LFU) Visit for safety assessments, even if they withdraw from dosing due to clinical failure.

Throughout the study, all patients will be monitored for signs and symptoms of cUTI or AP and the occurrence of adverse events. Laboratory data, including chemistry panels, complete blood counts, and samples for urine and blood cultures, as well as electrocardiograms (ECGs), will be collected from all patients at specified times throughout the study.

Sparse pharmacokinetic (PK) sampling (ie, a total of 5 samples per patient) will be performed to refine the population PK model. To maintain the blind, PK samples will be collected from both treatment groups. Samples obtained from the ETX2514SUL group will be analyzed using a validated assay by a central bioanalytical laboratory.

Patients will be enrolled in the study for approximately 21 days, with a maximum duration of study participation of 30 days. Screening procedures can be performed as standard of care within 48 hours prior to randomization on Day 1, with the exception of local laboratory serum creatinine determination, which must be obtained at the local laboratory within 24 hours of the first dose of study drug. The Treatment Period begins on Day 1, and study drug will be administered for 7 calendar days (or up to 14 days in patients with concurrent bacteremia). The EOT Visit will be completed on the final dosing day or the following day (allowing for a 1-day window to complete EOT procedures). The TOC Visit will be completed 7 days ( $\pm 1$  day) after the EOT for all patients. The LFU Visit will be completed 7 days ( $\pm 2$  days) after the TOC Visit for all patients.

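### Protocol 4.3 and 6.6 conflict on follow-up after early study withdrawal, and 3.1 limits follow-up after stopping drug to safety, so test-of-cure data may go uncollected

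*Protocol*

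**What the plan says.** The documents speak of two events.

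**Withdrawal from the study before study drug is complete.**
- Protocol 6.6: "For patients who are withdrawn from the study prior to completion of study drug, complete an EOT Visit at the time of study termination". Nothing after that visit is mentioned.
- Protocol 4.3, for premature withdrawal for any reason: every effort to complete "the full panel of assessments scheduled for the EOT Visit, and the patient should be followed through the LFU Visit". What that follow-up contains is not stated.
- For withdrawal after EOT, 6.6 asks sites to "complete the next scheduled visit (either TOC or LFU Visit) at the time of study termination", and 4.3 is similar.

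**Stopping study drug.**
- Protocol 3.1 (also the synopsis): such patients perform all End of "Treatment (EOT) Visit procedures and should be followed through the Late Follow-up (LFU) Visit for safety assessments". SAP 3.1 repeats this: they "should be followed through the Late Follow-up (LFU) Visit for safety assessments, even if they withdraw from dosing due to clinical failure".
- Protocol 7.7, for patients growing only Gram-positive organisms who are not improving and are taken off drug: they "should remain in the study to complete all study assessments".
- Protocol 3.1 and SAP 3.1 also set TOC at 7 days (±1) after EOT and LFU at 7 days (±2) after TOC, for all patients. Note 2 to SAP Table 1 says that after an early EOT no procedures are due until TOC.

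**What depends on it.** Missing TOC data give an indeterminate response: "Thus, patients with an indeterminate outcome are considered failures for the primary analysis" (Protocol 9.2.2.1; likewise SAP 8.2 and 8.11.1). Adverse events "will be monitored and documented from the time of informed consent until study participation is complete" (Protocol 8.1).

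**The concern.** Sections 4.3 and 6.6 address the same patient and give different instructions. One continues to LFU and the other ends with an EOT visit. For a patient who merely stops dosing, the general wording limits follow-up to safety, while the schedule gives every patient a TOC visit that includes a urine culture and a clinical outcome.

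The primary efficacy endpoint needs both of those TOC results. If a site does not collect them, a patient who was doing well at EOT and stopped for tolerability is scored as an efficacy failure. If the arms stop at different rates, the comparison shifts. Safety is the primary objective, and patients who stop because of an adverse event are those whose later course matters most. Under 6.6 their non-serious events may be observed for a shorter time than those of completers. Data not collected at TOC cannot be recovered at analysis.

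**Working it through.** The documents give no stopping rate, assumed success rate or power figure, so there is no plan figure to reproduce.

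**1. Is there a conflict?** For study withdrawal before completing drug, yes: 4.3 includes follow-up through LFU and 6.6 does not. For stopping drug, the conflict is milder. The safety-only phrase does not cancel the TOC visit, but it gives a site reason to omit the efficacy parts. Outside the 7.7 subgroup, no text says expressly that someone who stops drug completes the efficacy assessments.

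**2. Which patients change category?** Clinical failure at EOT carries to TOC (Protocol 6.4, 7.6; SAP 8.2), and so does microbiologic persistence at EOT (Protocol 7.8). Cure and eradication do not carry forward. Only patients who were neither a failure nor a persistence at EOT are affected. They become indeterminate and count as failures in m-MITT. If the clinical response is indeterminate, they also leave CE and hence ME; a missing TOC culture alone removes them from ME. A patient with fewer than 12 doses could not be a CE cure in any case (Protocol 9.1).

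**3. How much follow-up is at stake under 6.6?** EOT to LFU is 7 + 7 = 14 days nominally, and with the windows 6 + 5 = 11 to 8 + 9 = 17 days.

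**4. Effect per patient.** About 80 patients at 2:1 is about 53 and 27. Assume 70% to 100% enter m-MITT, that is 37:19 to 53:27. One success lost lowers the arm's rate as follows:
- active: 1/53 = 1.9 to 1/37 = 2.7 points
- placebo: 1/27 = 3.7 to 1/19 = 5.3 points

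**5. Bias on assumed rates.** Let *a* and *b* be the stopping rates on active and placebo, and *s* the success rate among stoppers in both arms, with all their TOC data lost. The difference then shifts by −(*a* − *b*) × *s*.

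With *a* = 10%, *b* = 3%, *s* = 60% and 80% success in completers:
- TOC collected: 0.90×0.80 + 0.10×0.60 = 78.0%; 0.97×0.80 + 0.03×0.60 = 79.4%; difference −1.4 points.
- TOC lost: 0.90×0.80 = 72.0%; 0.97×0.80 = 77.6%; difference −5.6 points.
- Shift: −5.6 − (−1.4) = −4.2 = −(0.07 × 0.60).

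| Stopping, active v placebo | *s* = 60% | *s* = 30% |
|---|---|---|
| 5% v 3% | 0.02×0.60 = 1.2 points | 0.02×0.30 = 0.6 points |
| 10% v 3% | 0.07×0.60 = 4.2 points | 0.07×0.30 = 2.1 points |

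**6. Against the precision available.** The interval is the difference ± [1.96 × √(p₁q₁/n₁ + p₂q₂/n₂) + 0.5 × (1/n₁ + 1/n₂)].
- At 42/53 v 22/27 (about 80% each, assumed): −2.2 ± (18.3 + 2.8) = −23.3 to 18.8 points.
- With three active successes lost, 39/53 v 22/27: −7.9 ± (18.86 + 2.80) = −29.5 to 13.8 points.

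**The case against.** The strongest reply is that different instructions for different events are not a contradiction. Protocol 3.1 and 7.7 speak of stopping drug, and 4.3 and 6.6 of leaving the study. That stands: a reader who counts four competing rules for one patient merges two events. The direct conflict is 4.3 against 6.6. The 3.1 wording is loose rather than contradictory.

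A reader might also infer that a site following 4.3 and then 6.6 stops at EOT. The documents do not support this, because 4.3 itself calls for follow-up through LFU, and 6.6 names a visit without forbidding later ones. The schedule also favours collection: TOC is set for all patients, and SAP Table 1 leads from an early EOT to TOC. The loss therefore arises only where a site applies 6.6, or the safety-only phrase, literally.

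Nor does the text support a general loss of later adverse events. Serious events are reportable, and liver tests monitored, to 30 days after the last dose (Protocol 8.3, 8.10). Clinically significant laboratory abnormalities are followed until they resolve, stabilise or lose significance (8.1). What remains exposed is non-serious events and the scheduled TOC and LFU laboratory tests.

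Finally, 60% success among stoppers may be too high. Cure requires that no further antimicrobial therapy be warranted, and no oral switch is allowed, so someone who stops very early and still needs antibiotics could hardly be a cure even if seen at TOC. That lowers the illustrated bias but leaves the conflict in the text.

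**Conclusion.** The point holds as a wording conflict with a real but limited consequence. Sections 4.3 and 6.6 disagree for patients withdrawn from the study before completing drug. The safety-only phrase in the synopsis, Protocol 3.1 and SAP 3.1 sits poorly with the TOC schedule and with 7.7. Literal application can cost primary-endpoint data for patients not already failing at EOT and, under 6.6, nominally 14 days of non-serious adverse events and scheduled laboratory tests.

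The bias of about 1 to 4 points rests wholly on assumed stopping rates, 60% success among stoppers and complete loss of their TOC data. A reader might take 4 points as an expected bias against the active arm, but nothing in the documents supports those rates. It is also small beside a half-width of about 21 points in an efficacy comparison that is descriptive and unpowered. The reason to act is that the text can be aligned cheaply and the data cannot be recovered later.

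**What to change.** Reconcile the synopsis, Protocol 3.1, 4.3, 6.6 and 7.7, and SAP 3.1, so that stopping study drug is distinguished from withdrawing from the study.

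- **Synopsis, Protocol 3.1, SAP 3.1:** replace the safety-only qualifier with wording that covers all scheduled safety and efficacy assessments through LFU. This also brings the general rule into line with 7.7.
- **Protocol 6.6:** add that patients who have not withdrawn consent to follow-up also complete the scheduled TOC and LFU Visits, as 4.3 already implies. Keep the visit at termination for withdrawal of consent and for termination by the sponsor or a regulator.
- **Protocol 8.4:** the early-termination procedures after a pregnancy should point to the same reconciled rule, so that no new conflict arises.
- **Protocol 4.3:** leave the reasons for ending drug or participation, and the investigator's judgement on them, unchanged.

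The cost is a protocol and SAP wording amendment and some follow-up visits that sites might otherwise have skipped. Sample size and analysis method do not change.
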